6/14/2021

Pleural Manometry for the Characterization of
Spontaneous and Tension Pneumothorax

NCT04630301

Date: 06/14/2021

Principal Investigator: [name]

Application Number: IRB00256185

JHM IRB - eForm A – Protocol

- **Use the section headings to write the JHM IRB eForm A, inserting the appropriate material in each. If a section is not applicable, leave heading in and insert N/A.**
- **When submitting JHM IRB eForm A (new or revised), enter the date submitted to the field at the top of JHM IRB eForm A.**

1. Abstract

A pneumothorax is defined as the presence of air within the pleural space. Patients can be asymptomatic, have mild dyspnea, or significant chest pain and dyspnea, and even hemodynamic instability in the case of a tension pneumothorax (TP).¹ The historical teaching for the cause of hemodynamic instability has been increased pressures within the pleural space causing a shift of the mediastinum, “kinking” of the inferior vena cava and a reduction in cardiac output. Expert guidelines define TP as when the intrapleural pressure (Ppl) is greater than atmospheric pressure for much of the respiratory cycle.² Therefore, it follows that Ppl in patients without tension remains below atmospheric pressure for much of the respiratory cycle. However, these manometric definitions remain controversial as Ppl in TP has never been measured and data on Ppl on hemodynamically stable patients is limited. There remains a gap in our current understanding of the pathophysiology of these disease processes. Exploring this unknown can be of clinical significance as pleural manometry is being employed in patients with pleural effusions to guide management. By using recently demonstrated pleural manometric techniques, this study aims to characterize the intrapleural pressures in patients with pneumothorax.

2. Objectives

Primary objectives:

1. Describe the intrapleural pressure throughout the respiratory cycle in patients with pneumothorax.

Secondary objectives:

1. Demonstrate a relationship between initial intrapleural pressure and presence of persistent air leaks, need for prolonged chest tube drainages, pleurodesis, intrabronchial valve (IBV) placement, and/or video-assisted thorascopic surgery (VATS).

3. Background

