The rate of hospitalization for spontaneous pneumothorax among people age 14 or older is approximately 227 per million.³ Spontaneous pneumothorax in the absence of trauma can be further classified as primary spontaneous pneumothorax (PSP) or secondary spontaneous pneumothorax (SSP) based on the absence or presence of underlying structural lung disease, respectively. Though recent studies suggest that in some cases conservative management with close observation is an acceptable treatment, definitive evacuation remains a cornerstone of management for patients who are symptomatic or who have a large pneumothorax.⁴ Intrapleural

Date: 06/14/2021

Principal Investigator: [name]

Application Number: IRB00256185

air can be removed by either needle aspiration or introduction of a watersealed catheter into the pleural space. In the event of TP, emergent chest thoracostomy is preferred. In all cases, the goal of treatment remains to re-expand the affected lung, after which the catheter may be removed. If the visceral pleural defect is not healed after 5 days, it is deemed a persistent air leak. In these cases, the chest tube is maintained and more aggressive measures such as pleurodesis, placement of an IBV, or VATS are performed. Unfortunately, there is currently no method to predict which patients will require these more invasive procedures.

The lack of prognostic indicators is not the case in pleural effusions, however. Pleural manometry has been shown to be a useful tool in the management of patients with effusions. Doelken et al. described using an overdamped water manometer or an electronic transducer connected to a thoracentesis catheter for the direct measurement of Ppl with similar accuracy.⁵ Traditionally, thoracenteses are aborted after onset of dyspnea or cough, all fluid is drained, or 1L of fluid has been removed. This 1L limit exists to avoid the feared complication of reexpansion pulmonary edema. However, monitoring of Ppl during drainage and aborting the procedure once Ppl drops below -20 cmH₂O allows for safe drainage of often larger volumes.⁶⁻⁷ Furthermore, Lan et al. demonstrated that Ppl could diagnose non-expandable lung and predict pleurodesis failure in patients with malignant effusion.⁸ Lee et al, recently reported the use of a simple, in-line, digital manometer to measure Ppl in patients with pleural effusion.⁹

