Criteria for recruitment into this study include patients aged 18 or older admitted with clinical or radiographic evidence of new pneumothorax who are referred to Interventional Pulmonology for needle aspiration or tube thoracostomy. TP will be defined as a pneumothorax that results in mean arterial pressure <65 or systolic BP < 90.

Exclusion criteria include bilateral pneumothorax and pregnancy.

6. Drugs/ Substances/ Devices

No medical drugs, substances, or devices are being studied.

7. Study Statistics

- a. Primary outcome variables: Inspiratory Ppl, Expiratory Ppl, and Mean Ppl.
- b. Secondary outcome variables: Duration of chest tube placement, referral for pleurodesis, IBV placement, and/or referral for VATS.

Date: 06/14/2021

Principal Investigator: [name]

Application Number: IRB00256185

- c. Statistical plan: A student's t-test will be used to determine statistical significance in differences of Ppl between SP and TP. A student's t-test will be used to determine statistical significance in differences of Ppl in the secondary outcomes listed above. A sample size of 100 SP and 25 TP will be used based on expected incidence of disease in recruitment period. Enrollment will be competitive across all sites and the Coordinating Center (JHU's IP research team) will immediately alert PIs and Study Coordinators at the other sites if enrollment is paused or completed.
- d. Early stopping rules: Consistent inability to measure Ppl in TP. If study is stopped early, all sites will immediately be notified by JHU's IP research team to terminate enrollment.

8. Risks

- a. Enrolled patients will be only those already planned to receive chest tubes or needle aspiration; therefore, this study poses the same risks as these standard procedures. These risks include bleeding, infection, and local tissue damage. The study may delay evacuation of pneumothorax up to 30 seconds while Ppl are being recorded. These risks are independent of participation or non-participation in our study. No provisions are made for a research study-specific injury to the subject.
- b. Risks will be mitigated by using the same standard of care for chest tube or needle aspiration. Overall, the delay in chest tube placements will be minimized and negligible by limiting measurement time to 30 seconds.

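### The secondary Ppl-outcome test has no separation of, or adjustment for, SP and TP, so an apparent association could come from the group mix alone

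*Combined protocol and SAP*

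**What the plan says.** The secondary objective (section 2) is to "Demonstrate a relationship between initial intrapleural pressure and presence of persistent air leaks, need for prolonged chest tube drainages, pleurodesis", valve placement or VATS. It is not restricted to SP or to TP.

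Section 7c gives two tests. The first names its groups: "A student's t-test will be used to determine statistical significance in differences of Ppl between SP and TP". The second does not. It is a Student's t-test of "differences of Ppl in the secondary outcomes listed above. A sample size of 100 SP and 25 TP will be used", where the text passes straight from the test to the sample size. No stratification, covariate, SP-only analysis or analysis set is given for it there or elsewhere.

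On numbers, 7c says: "A sample size of 100 SP and 25 TP will be used based on expected incidence of disease in recruitment period". No power calculation is given.

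Three other places bear on the point. Section 5 defines TP by blood pressure, not by pleural pressure. The abstract reports that "Expert guidelines define TP as when the intrapleural pressure (Ppl) is greater than atmospheric pressure for much of the respiratory cycle", but calls such definitions controversial because Ppl in TP has not been measured. Section 4a recruits iatrogenic cases alongside spontaneous and tension cases, and 7c does not say in which of its two groups they are counted.

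**The concern.** SP/TP status may be tied to both sides of the secondary comparison. On the guideline definition, Ppl would be expected to be higher in TP. A patient hypotensive from a pneumothorax may also have a different course, in either direction. If both hold, patients with an outcome contain a different share of TP from patients without it, and their mean Ppl differs for that reason alone.

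This matters because of the use the background has in mind. Section 3 says that "there is currently no method to predict which patients will require these more invasive procedures", and Ppl is put forward as a candidate. TP is recognised from blood pressure without a manometer. A pooled association that only re-expresses TP status would not show that measuring Ppl adds anything. The evidence cited in section 3 for a link between Ppl and prolonged drainage comes from spontaneous pneumothorax, so a pooled test does not put quite the same question.

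**Working it through.** **Inputs from the plan.** 100 SP and 25 TP (7c), total 125, TP share 25/125 = 20%. Student's t-test (7c). The plan gives no alpha, SD, effect size or outcome rate, so there is no power figure to reproduce.

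**Assumptions.** Two-sided alpha 0.05. Ppl is normal with the same SD in both groups, and mean Ppl in TP is shifted by d SD. The outcome is binary, with rate p_SP or p_TP. Within each group Ppl and outcome are unrelated, so every significant result is false.

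**Step 1: the pooled difference produced by mix alone.**

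Expected difference = d × (TP share among patients with the outcome − TP share among those without).

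With 20% in SP and 40% in TP:
- With the outcome: 20 SP + 10 TP, TP share 10/30 = 0.333.
- Without: 80 SP + 15 TP, TP share 15/95 = 0.158.
- Difference in share: 0.333 − 0.158 = 0.175.

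Each 10 cmH2O by which TP exceeds SP therefore creates a pooled difference of about 1.75 cmH2O.

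With 30% in SP and 15% in TP, the shares are 3.75/33.75 = 0.111 and 21.25/91.25 = 0.233. The difference is −0.122, so the sign reverses.

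**Step 2: how often the test is significant.** Simulation, 4,000 trials per scenario. The Monte Carlo standard error at 5% is √(0.05 × 0.95/4000) = 0.3 percentage points.

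| TP shift in Ppl (SD) | Outcome rate SP / TP | Pooled difference from mix (SD) | Pooled test | Adjusted for SP/TP | SP only |
|---|---|---|---|---|---|
| 0 | 20% / 40% | 0 | 4.4% | 4.4% | 4.8% |
| 1 | 30% / 30% | 0 | 5.3% | 4.7% | 5.0% |
| 1 | 20% / 30% | 0.09 | 7.0% | 4.5% | 4.8% |
| 2 | 20% / 30% | 0.19 | 12.1% | 4.8% | 5.0% |
| 0.5 | 20% / 40% | 0.09 | 7.3% | 5.2% | 5.0% |
| 1 | 20% / 40% | 0.175 | 12.8% | 4.9% | 5.3% |
| 2 | 20% / 40% | 0.35 | 26.1% | 5.0% | 5.2% |
| 1 | 20% / 50% | 0.25 | 22.5% | 5.0% | 5.4% |
| 2 | 20% / 50% | 0.50 | 48.6% | 4.8% | 4.6% |
| 1 | 30% / 15% | −0.12 | 8.2% | 4.8% | 4.8% |
| 2 | 30% / 15% | −0.24 | 14.0% | 4.8% | 5.0% |

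A separate simulation of 6,000 trials per scenario gave 7.5% and 11.1% for 20%/30%, and 13.8% and 25.8% for 20%/40%, at shifts of 1 and 2 SD. Over all scenarios run, the adjusted and SP-only tests stayed between 4.4% and 5.8%.

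**Step 3: precision given up.**
- SP only against all 125 at equal event rates: √(125/100) = 1.12, an interval about 12% wider.
- SP only against the stratified analysis with 20 + 10 events: information is n·p·(1 − p), which is 100 × 0.2 × 0.8 = 16 in SP and 25 × 0.4 × 0.6 = 6 in TP. √(22/16) = 1.17, about 17% wider.
- Detectable difference at 80% power, (1.96 + 0.84) × √(1/n₁ + 1/n₀): if 30% have the outcome, 0.55 SD for 125 patients and 0.61 SD for 100 SP; if 20%, 0.63 and 0.70 SD. For 25 TP alone it is 1.22 and 1.40 SD, so a TP-only result can only be descriptive.

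**The case against.** The strongest reply is that the pooled analysis may be the one the objective asks for. Section 2 speaks of pneumothorax in general. The abstract's traditional account is that raised pleural pressure lowers cardiac output, so TP status may partly result from high Ppl. Conditioning on it then answers a within-group question and may set aside the highest pressures. This stands. It is a reason to report the pooled result, labelled for what it is, and not to bar it. It does not remove the need to show whether Ppl says anything once TP is known.

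Second, the two conditions for bias are not established. Higher Ppl in TP is an expectation drawn from a guideline definition, not a hypothesis the protocol states, and nothing in the documents says that TP patients are drained longer or referred more often. This also stands: the bias could be negligible or run the other way.

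Third, 7c does not say that the groups are pooled. That is correct. Pooling is inferred from the absence of any named group in the second test, when the first test names both.

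A reader might also infer that the 4:1 mix was engineered, with a TP quota filled on purpose. The documents do not support this: the numbers are said to be "based on expected incidence of disease in recruitment period". Nor does the argument need it, since any mix of two groups that differ in both respects will do.

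**Conclusion.** The point holds as a gap in the secondary analysis. No separation of or adjustment for SP/TP is specified, and on the natural reading a Ppl-outcome difference can arise, or a true one be masked, through group mix alone.

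The size depends wholly on assumed figures. The false-positive rate is about 13% and 26% (TP Ppl 1 and 2 SD higher) with outcome rates of 20% against 40%, and about 7% and 12% with 20% against 30%. It stays near 5% if the groups differ in only one of Ppl and outcome rate. With fewer TP events the bias is negative and could hide a true positive association. The calculation covers binary outcomes. Duration of chest tube placement is continuous, and 7c does not say how a t-test of Ppl would be formed for it.

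A reader might go further and infer that the pooled result will be a false positive, or is invalid for the stated objective. The documents support neither: they give no Ppl values or outcome rates for TP, and the objective is not confined to SP. The primary SP-TP comparison is unaffected. This is worth correcting because the remedy is cheap, but its reach is a secondary objective.

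**What to change.** Amend 7c along these lines:

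*Each secondary comparison of Ppl by outcome will also be estimated with SP/TP status as a stratum or covariate, and in SP patients alone. Any statement that Ppl predicts outcome beyond what blood pressure already shows will rest on these estimates. The pooled comparison will be reported alongside, labelled as unadjusted for SP/TP. Results within TP alone will be descriptive.*

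State also which group iatrogenic cases belong to; without that, the SP analysis set is not defined.

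No new data are needed, since SP/TP status is already required for the primary comparison. The costs are the lower precision of the SP-only estimate (about 12% to 17% wider intervals, as worked above), which the stratified analysis mitigates by using all patients, and the need to say plainly that the adjusted result answers a within-group question.

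### Section 7d stops enrolment of the whole study when Ppl cannot be measured in TP, cutting short non-tension work that could still be completed, without a stated reason

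*Combined protocol and SAP*

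**What the plan says.** Section 7d contains one stopping rule, followed by its only stated consequence: "Early stopping rules: Consistent inability to measure Ppl in TP. If study is stopped early, all sites will immediately be notified by" the coordinating research team, so that they end enrolment. No sentence closes the TP group alone or keeps the other group open. The word describing how regular the failure must be is given no count, proportion or time point.

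Section 7c sets the group sizes: "A sample size of 100 SP and 25 TP will be used based on expected incidence of disease in recruitment period". It also has the coordinating centre alert sites when enrolment is paused or completed, again without distinguishing groups.

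The primary objective in Section 2 is not confined to tension: "Describe the intrapleural pressure throughout the respiratory cycle in patients with pneumothorax". The secondary objective is "Demonstrate a relationship between initial intrapleural pressure and presence of persistent air leaks, need for prolonged chest tube drainages", and then pleurodesis, valve placement and VATS; it does not mention TP either. The Abstract gives both gaps as motivation: "Ppl in TP has never been measured and data on Ppl on hemodynamically stable patients is limited".

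**The concern.** The trigger and the consequence differ in scope. The trigger concerns one group, planned at a fifth of the sample; the consequence falls on all of it. The Background describes measurement in spontaneous pneumothorax as practical and says that pressures in TP have not been reported, so the protocol's own feasibility doubt lies mainly with TP. A site following 7d would nevertheless turn away a stable patient after the stop, even if the measurement was working in such patients.

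At stake are the precision of the description of Ppl in non-tension patients and the number of patients available to relate initial Ppl to later drainage and procedures. How failures should be counted is a separate matter. It enters here only because it decides when a stop would occur.

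**Working it through.** **Nothing to reproduce.** The documents give no alpha, power, SD, precision target or trigger count. The group sizes rest on expected incidence. The check is therefore mainly textual, with arithmetic to show scale.

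**Which parts of the plan need TP**

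- Primary objective and the 7a variables ("Primary outcome variables: Inspiratory Ppl, Expiratory Ppl, and Mean Ppl"): the TP part needs TP patients; the non-tension part does not.
- 7c, t-test of SP against TP: needs TP.
- Secondary objective and the 7c t-tests of Ppl by the 7b outcomes: can be done without TP, though TP patients would otherwise contribute, since 7c does not restrict these tests to SP.
- Section 4j: already removes an individual whose Ppl cannot be measured reliably within 30 seconds, and 4k keeps that person on standard care. A single failure is therefore handled without stopping the study.

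**Planned shares (7c).** Total = 100 + 25 = 125. TP share = 25/125 = 20%. SP share = 100/125 = 80%. SP:TP = 4:1.

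**SP enrolled when the rule fires.** Assumption: the groups accrue in the planned 4:1 ratio. After k failed TP attempts, SP enrolled = 4k and SP forgone = 100 − 4k. As k is not given, a range is shown.

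**Precision.** 95% CI half-width for mean Ppl in SD units = t(0.975, n − 1)/√n.

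| k | SP enrolled | SP forgone | Half-width (SD) |
|---|---|---|---|
| 3 | 12 | 88 | 0.64 |
| 5 | 20 | 80 | 0.47 |
| 10 | 40 | 60 | 0.32 |
| 15 | 60 | 40 | 0.26 |
| 20 | 80 | 20 | 0.22 |
| no stop | 100 | 0 | 0.20 |

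**Secondary comparisons.** Assumptions: two-sided alpha 0.05, 80% power, and 20% of patients with the outcome. The detectable standardised difference is (1.96 + 0.84) × √(1/a + 1/b), where a and b are the numbers with and without the outcome.

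- n = 100: a = 20, b = 80, giving 2.80 × 0.250 = 0.70 SD.
- n = 60: a = 12, b = 48, giving 2.80 × 0.323 = 0.90 SD.
- n = 40: a = 8, b = 32, giving 2.80 × 0.395 = 1.11 SD.
- n = 20: a = 4, b = 16, giving 2.80 × 0.559 = 1.57 SD.

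If 10% to 40% have the outcome, the range is 0.93 to 0.57 SD with 100 SP and 2.09 to 1.28 SD with 20. The formula uses the normal approximation, so the values for the smallest groups are rough.

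**The case against.** The best defence is that this is a deliberate choice. Tension is in the title, the Abstract builds its case on the manometric definition of tension, the Background ends on the absence of TP measurements, and the first test in 7c is SP against TP. A sponsor could reasonably decide that, without TP, the study mostly extends work it already cites. That is a legitimate position, but the protocol does not state it. The Abstract also calls data in stable patients limited, and neither written objective depends on TP.

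A second argument is that the same manometer, needle and time limit serve every patient, so consistent failure in TP might point to the technique. This stands in part. A reader might infer that the trigger carries no information about other patients; the documents do not support that. It is a reason to check measurement in SP before continuing, not a reason to end SP enrolment automatically.

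Three further inferences go too far:

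- That only the SP-TP comparison would be lost. The description of Ppl in TP is part of the primary objective and is lost as well.
- That a stop discards the SP data. 7d ends enrolment; nothing says that data already collected are dropped or left unanalysed.
- That SP means the same as non-tension. Section 4a also recruits iatrogenic cases, and Section 5 defines TP by blood pressure, so a spontaneous case can be TP. Any rewording has to respect this.

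**Conclusion.** The point holds as a mismatch of scope. A feasibility failure in 20% of the planned sample would, on the plain reading of 7d, end enrolment everywhere, although the non-tension description and the Ppl-outcome relationship could still be completed. 7d does not name SP, so this rests on the ordinary meaning of stopping the study and on the absence of any group-specific alternative.

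The size depends on a trigger that the plan does not define and on the assumed 4:1 accrual. A stop after 3 to 10 failures would forgo 88 to 60 of the 100 SP. After 15 or 20 it would forgo 40 or 20, and at 20 the half-width of 0.22 SD is close to the 0.20 SD at full size. A reader might infer that a stop breaches a required precision. It does not: the 100 came from expected incidence, and the plan sets no such requirement.

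This is a cheap improvement, not a flaw that undermines the study. Confidence is moderate, because the benefit arises only if the rule fires, and mainly if it fires early.

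**What to change.** Reword 7d along these lines: *If Ppl consistently cannot be measured in TP, study enrolment of TP patients closes at all sites. Enrolment of the SP group, as counted in 7c, continues to the planned 100 within the enrolment period, unless measurement is also failing in that group.*

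State in 7c whether non-tension iatrogenic cases count towards the 100. State that the report will give the number of TP attempts and failures, and will present the SP-TP comparison as not estimable or as based on the few TP patients measured. Make the pause and completion alert in 7c group-specific. If a whole-study stop is intended, keep it and give the reason.

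The cost is a protocol amendment across sites, each with its own IRB approval under Section 4b. No patients are needed beyond those planned. The downside is that, if TP closes, the study runs on without its TP comparison.
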